#### **8.2.2.2 Cough Severity Diary**

Participants will be asked to record their cough frequency, intensity, and disruption due to cough using the 7-item CSD. Participants will rate each item using an 11-point scale ranging from 0 to 10 with higher scores indicating greater severity.

Participants will complete the CSD at approximately the same time daily, beginning at Visit 1 until Visit 9 (with a minimum requirement of 7 days of completion prior to first dose of study intervention/Randomization).

During the Extension study period, completion of the CSD will be required daily, at approximately the same time for a 1 week period, beginning 1 week prior to Visit 11 and beginning 1 week prior to Visit 13. Participants should be contacted (eg, by telephone or text) during the Extension study period to remind them to complete the CSD during these weeks.

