## 3 Hypothesis, Objectives, and Endpoints

Objectives	Endpoints
Exploratory	

Objective: To evaluate the off-treatment durability after 1 year of treatment with MK-7264, over the course of 3 months off treatment

	

Cough Severity VAS

LCQ

CSD

PGIC

EQ5D-5L

Objective: To evaluate the time to “loss of response” in on-treatment responders over the course of 3 months off treatment

	

Time to loss of response based on VAS

Time to loss of response based on CSD

Time to first use of a medication for cough

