### 9.4 Analysis Endpoints

The main analyses will be performed in all subjects who enter the Off-treatment Durability Study Period. It is acknowledged that this population will include participants with varying measures of cough impact and severity as assessed by the ePROs both at the end of the 1-year treatment (ie, Week 52), as well as compared to prestudy baseline (ie, Week 0).

The primary metric of treatment durability will compare the ePRO measurement after 12 weeks off-treatment, to the measurement at Week 52 (ie, immediately prior to treatment discontinuation), and will specifically seek to describe the proportion of participants who either fail to maintain their treatment response, or who maintain treatment response.

One way to describe “failure to maintain the response” for a given ePRO, as an example, is that either the 12 weeks off-treatment measurement is decreased by at least X% of the Week 52 response, or the participant needs treatment for cough. The actual threshold would be based on considerations about clinically important differences and real-world data experiences. The definition will be specific to each ePRO.

In addition, the data will be explored to examine the impact of on-treatment response to MK-7264 on the outcome measures described above. Specifically, the on-treatment measurement (defined as the difference in the Week 52 measurement compared to Week 0) will be categorized using different threshold definitions of “response”, and the subsequent off-treatment ePRO measurement in the Off-treatment Durability Study Period will be explored as a function of the on-treatment response.

One way to describe the “on-treatment response” for VAS, as an example, is that a participant has a Week 52 measurement at least X-mm lower than the Week 0 measurement. The definition will be specific to each ePRO.

The final details about the analysis endpoints, as well as other aspects of the analyses, will be documented in an Off-treatment Durability Study Period memo, separate from the treatment period supplemental SAP, to be finalized before the completion of the Off-treatment Durability Study Period.

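### Appendix 7 uses the Week 52 score both to define on-treatment response and as the reference for off-treatment change, so responder-based durability estimates contain regression to the mean

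*Combined protocol and SAP*

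**What the plan says.** Appendix 7 adds a 3-month off-treatment period for about 150 participants pooled from P027 and P030, drawn from any of the three arms. Its Section 9.4 sets the main durability metric as a comparison: "compare the ePRO measurement after 12 weeks off-treatment, to the measurement at Week 52". The example of failure to maintain response, apart from needing cough treatment, is that "the 12 weeks off-treatment measurement is decreased by at least X% of the Week 52 response".

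The same section then plans to explore those outcomes by on-treatment response: "the on-treatment measurement (defined as the difference in the Week 52 measurement compared to Week 0) will be categorized". The VAS example is that "a participant has a Week 52 measurement at least X-mm lower than the Week 0 measurement". Section 3 of the appendix adds an objective on time to loss of response, "in on-treatment responders over the course of 3 months off treatment".

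Three statements limit the reach of the point. Section 9.4 also says: "The main analyses will be performed in all subjects who enter the Off-treatment Durability Study Period". Sections 9.3 and 9.8 rule out hypothesis testing, although Section 9.3 promises point estimates and, as appropriate, 95% confidence intervals. The thresholds (X) are blank, and final details are left to a memo due before the durability period is completed.

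The appendix describes no separate qualifying measurement and no contrast between arms. Its Section 9.5 bases analyses on all enrolled, and Section 9.10 plans no subgroup analysis.

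**The concern.** A Week 52 score is the participant's underlying level plus variation particular to that occasion. Some participants pass a response threshold partly because Week 52 was a good reading. Twelve weeks later that favourable part is not expected to recur, so on average they score worse, whatever withdrawal does. Participants who just missed the threshold tend to score better. Within a group selected on Week 52, no average change from Week 52 is therefore not what absence of a withdrawal effect looks like.

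Whether responders lose their response off drug is one of the appendix's two objectives. The artefact exaggerates loss among responders and builds in a link between better on-treatment response and greater later loss. A confidence interval does not reveal this. The planned Clopper-Pearson interval (for example 120 of 150: 72.7% to 86.1%) reflects sampling error only.

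**Working it through.** The plan gives no figure on this point to reproduce, so the check is of direction and plausible size, always with no withdrawal effect.

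**Inputs.** From the documents: response cuts of 1.3 points (LCQ) and 30 mm (VAS), borrowed from main Section 9.4.3 because Appendix 7 leaves X open. Assumed, and not in the documents: score SD 3.5 (LCQ) and 20 mm (VAS); true on-treatment improvement of mean 2.5, SD 2.5 (LCQ) and mean 25 mm, SD 20 mm (VAS); reliability r of 0.7 to 0.9; independent errors between visits.

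**Formulas.** Error variance v = (1 − r) × SD². Observed improvement from Week 0 to Week 52 has SD S = √(s² + 2v), where s is the SD of true improvement. With cut c and mean improvement m, a = (c − m)/S. The favourable Week 52 error expected in responders, which is also their apparent later worsening, is (v/S) × φ(a)/[1 − Φ(a)]. The apparent gain in non-responders is (v/S) × φ(a)/Φ(a).

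| Measure, r | v | S | a | φ/(1 − Φ) | Responders worsen by | Non-responders improve by |
|---|---|---|---|---|---|---|
| LCQ, 0.7 | 0.3 × 12.25 = 3.675 | √(6.25 + 7.35) = 3.69 | −0.325 | 0.603 | 0.60 | 1.0 |
| LCQ, 0.9 | 0.1 × 12.25 = 1.225 | √(6.25 + 2.45) = 2.95 | −0.407 | 0.558 | 0.23 | 0.4 |
| VAS, 0.7 | 0.3 × 400 = 120 | √(400 + 240) = 25.3 | 0.198 | 0.928 | 4.4 mm | 3.2 mm |
| VAS, 0.9 | 0.1 × 400 = 40 | √(400 + 80) = 21.9 | 0.228 | 0.949 | 1.7 mm | 1.2 mm |

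Simulation of the same model agrees. It gives a mean change of 0.0 in all entrants, and 0.0 in responders when they are classified on Week 38 with Week 52 kept as the reference.

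**A proportion, closer to what is planned.** Taking X as 30% for illustration, the share of responders falsely counted as having lost at least 30% of the Week 52 response is:

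| Measure, r | Classified on Week 52 | Classified on Week 38 |
|---|---|---|
| LCQ, 0.7 | 37% | about 31% |
| LCQ, 0.9 | 26% | about 22% |
| VAS, 0.7 | 25% | about 18% |
| VAS, 0.9 | 9% | about 6% |

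The part due to selection is thus about 3 to 7 percentage points. The rest is ordinary within-person noise.

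**Sensitivity to the model.** A second VAS model (assumed: Week 0 mean 68, SD 14, truncated at 40; on-treatment mean 40, SD 25) gives responder worsening of 6.3, 4.2 and 2.1 mm at within-person correlations 0.7, 0.8 and 0.9. At 0.8, 23% of responders lose at least 30% while only 11% gain as much. Pure noise around a fair reference would not be so lopsided.

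**Cost of classifying on Week 38.** In the first model, 12% to 18% (LCQ) and 16% to 23% (VAS) of Week 38 responders are already below the cut at Week 52 while still on treatment. For LCQ, 3% to 9% have a Week 52 response of zero or less.

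**Availability.** CSD and VAS are completed daily for one week, "beginning 1 week prior to Visit 11 and beginning 1 week prior to Visit 13" (the VAS section has the same schedule). Main Section 8.2.2 lists Visit 11 among the visits at which ePROs are activated, and the Schedule of Activities continues LCQ into the extension. EQ5D-5L has no Week 38 value but is collected at Week 24. Entrants must have completed both periods on study intervention through the evening before Visit 13, so Weeks 24 and 38 are on-treatment for all of them.

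**The case against.** The strongest reply has four parts.

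- **Scope.** The main analyses use all entrants, where the mean change is unbiased. The responder split is an exploratory addition with placeholder rules. This stands and limits the point. The thresholds are open, but using Week 52 both to classify and as the reference is stated as what will be done.
- **No test is planned.** A reader might infer that the design yields false-positive findings at a high rate. In the first model, a responder mean-change interval would exclude zero in 14% to 65% of trials of 60 to 150 entrants, and a responder versus non-responder test would reach significance in 23% to 95%. The documents do not support that reading: they plan neither analysis, only a proportion with an exact interval and Kaplan-Meier summaries. What remains is bias in estimates, not inflated test error.
- **Most false loss is noise.** Also true. Reclassification removes only 3 to 7 points.
- **Week 52 is the natural start for durability.** It is the last score before treatment stops. A reader might conclude that Week 38 should replace it throughout. That would be wrong for time to loss of response, which would then begin with a sizeable minority who have no response left to lose. A percentage of the Week 52 response also has no meaning where that response is zero or negative.

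Entry requires the Visit 13 LCQ but not the Visit 11 LCQ, and the P027 visit schedule is not in these documents. Both reservations stand.

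**Conclusion.** The concern holds for the analysis of off-treatment change by on-treatment response, and for time to loss of response on VAS and CSD in responders. The direction follows from the definitions: apparent loss in responders and apparent gain in non-responders, without any withdrawal effect. Size cannot be derived from the documents. Under the first model and reliability 0.7 to 0.9 it is about 0.2 to 0.6 LCQ points (against the plan's 1.3-point responder threshold) and 2 to 4 mm VAS in responders, with about 3 to 7 percentage points of false 30% loss. The second VAS model gives 2 to 6 mm over the same range. If the Week 52 VAS is a weekly mean, which Appendix 7 does not say, the artefact shrinks but does not vanish.

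Mean change in all entrants is unaffected. So are PGIC, which the durability schedule collects only at Visit 17 or discontinuation, and time to first cough medication as a measure in itself. The point does not bear on the Main or Extension period results. It is a cheap improvement to an exploratory analysis whose memo, under the plan, can still be written accordingly.

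**What to change.** In Appendix 7 Section 9.4 and the durability memo:

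1. For the exploratory analysis of off-treatment change as a function of on-treatment response, classify response on Week 38 (Visit 11) minus Week 0 for LCQ, mean weekly CSD and VAS, and on Week 24 minus Week 0 for EQ5D-5L. Keep Week 52 as the reference for change.
2. For time to loss of response, keep the Week 52 definition of responder and add the Week 38 classification as a sensitivity analysis.
3. Report both sets of results by randomised arm, with placebo entrants as the reference for regression to the mean.

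The cost is a few sentences and no new P030 data. The downsides should be stated in the memo:

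- About 12% to 23% of Week 38 responders (same assumptions) are no longer responders at Week 52.
- Some entrants may lack a Visit 11 score.
- Matching visits in P027 must be confirmed.
- Some artefact remains if within-person correlation decays over time, which is why the placebo reference is needed.
- Arms will be small: an even split of 150, which nothing guarantees, would give 150/3 = 50 per arm over both studies, and fewer responders. The placebo shift is a guide and not an exact correction, because selection is more extreme where mean response is lower.

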## 9 Statistical Analysis Plan

### 9.2 Responsibility for Analyses/In-house Blinding

The Main Period of the phase 3 study will be completed while the Extension Study Period and Off-treatment Durability Study Period are ongoing. Selected members of the Sponsor study team may be unblinded to review the data from the Main Study Period and author a CSR for facilitating regulatory submission.

A final database lock will occur after all participants have completed the Extension Study Period. This database lock will occur independent of enrollment into the Off-treatment Durability Study Period. The data from the Off-treatment Durability Study Period will be summarized in a separate report from the Main and Extension Study Period data.

The investigator site personnel and the participants will be blinded to intervention assignment until the entire study is completed.

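### The cut-off behind the primary durability metric is open and may be set at any time before the durability period ends, by authors not barred from the off-treatment data

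*Combined protocol and SAP*

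**What the plan says.** Appendix 7 Section 9.4 defines the primary metric by comparing each questionnaire after 12 weeks off treatment with its Week 52 value. The plan "will specifically seek to describe the proportion of participants who either fail to maintain their treatment response, or who maintain treatment response". The analysis set is everyone who enters: "The main analyses will be performed in all subjects who enter the Off-treatment Durability Study Period". Appendix 7 Section 9.6.1 then reports, separately for each questionnaire, the proportion maintaining response with a Clopper-Pearson 95% interval.

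The cut-off is a placeholder. As an example, failure means that "either the 12 weeks off-treatment measurement is decreased by at least X% of the Week 52 response", or that the participant needs treatment for cough. On how X will be chosen, Section 9.4 says: "The actual threshold would be based on considerations about clinically important differences and real-world data experiences". Final details go into a memo, separate from the treatment-period supplemental SAP, "to be finalized before the completion of the Off-treatment Durability Study Period".

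Appendix 7 Section 1.1 puts the calendar length of the period at about 16 months from first entry to last call. VAS and CSD are recorded daily throughout (Appendix 7 Sections 1.3 and 8.2.2).

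**The concern.** The deadline is a stated timing rule, not a missing detail, and it falls at the end of data collection. A memo signed in the last weeks would comply in full. By then most of the off-treatment data could exist, and the documents do not say that the authors must not have looked at them.

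The reported proportion depends directly on X. If X is chosen with the data in view, the Clopper-Pearson interval describes sampling error only and leaves out the effect of the choice. The two time-to-loss-of-response endpoints in Appendix 7 Section 3 (VAS and CSD) share the problem, because they also need a definition of loss.

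Elsewhere the plan is stricter, and not only for confirmatory work. Main Section 9 ties documented changes to exploratory analyses to the time before unblinding. Main Section 9.5.1 fixes the per-protocol population before first unblinding. Main Section 9.6.2 fixes the taste-related AE definition before the Main-period lock. The durability memo has no comparable anchor.

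**Working it through.** **No plan figure to reproduce.** The target of about 150 participants across P027 and P030 (Appendix 7 Section 9.9) has no stated precision target or assumed proportion. That is not an error. The checks below ask how much data could exist when the memo is signed, and how far X moves the result.

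**1. Data available before the deadline**

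Inputs from the documents: 16 months in total; follow-up from Day 365 to Day 449, so 449 − 365 = 84 days = 12 weeks. With 365.25/12 = 30.44 days per month, follow-up is 84/30.44 = 2.76 months. The entry window is then 16 − 2.76 = 13.24 months.

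The entry pattern is not given, so two are assumed. With uniform entry, the share with complete 12-week data b months before the end is (16 − b − 2.76)/13.24. With entry rate rising linearly (late-loaded), it is the square of that share.

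| b (months before end) | Uniform | Late-loaded |
|---|---|---|
| 3 | 10.24/13.24 = 77% | 60% |
| 2 | 11.24/13.24 = 85% | 72% |
| 1 | 12.24/13.24 = 92% | 85% |
| 0.5 | 12.74/13.24 = 96% | 93% |

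**2. Effect of X on the proportion**

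Assumption: the retained share of the Week 52 response is normal with mean m and SD s. A participant maintains response if the loss is below X, that is, if the retained share exceeds 1 − X. The proportion maintaining is 1 − Φ((1 − X − m)/s).

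| m, s | X = 20% | X = 50% | Shift |
|---|---|---|---|
| 0.5, 0.3 | 1 − Φ(1.00) = 16% | 50% | 34 points |
| 0.5, 0.5 | 1 − Φ(0.60) = 27% | 50% | 23 points |
| 0.7, 0.3 | 1 − Φ(0.33) = 37% | 1 − Φ(−0.67) = 75% | 38 points |
| 0.7, 0.5 | 1 − Φ(0.20) = 42% | 1 − Φ(−0.40) = 66% | 24 points (23 before rounding) |

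**3. Sampling error for comparison**

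Clopper-Pearson at 75/150 gives 41.7% to 58.3%, a half-width of 8.3 points. For proportions from 30% to 80% at n = 150 the half-width is 6.7 to 8.3 points.

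**4. Allowing for the cough-treatment route**

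Participants who fail by needing cough treatment fail at every X. If a share q fails that way, independently of retained response, the shift is multiplied by 1 − q. At an illustrative q = 50%, the 23 to 38 points become 23 × 0.5 = 11.5 to 38 × 0.5 = 19 points. The documents give no value for q.

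**Limit of the model.** A percentage of the Week 52 response is unstable or undefined for entrants with little or no response, and placebo participants may enter. The figures show how sensitive the proportion can be; they do not predict it.

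**The case against.** The best defence is that nothing confirmatory is touched. Both durability objectives are exploratory (Appendix 7 Section 3), no hypothesis is tested (Section 9.3), no interim analysis is planned (Section 9.7), and the results go into a separate report. A memo due before the period completes is already promised. Data held in an eDiary system are not the same as data that the authors have examined. All of this stands, and it keeps the severity low. It does not supply the missing rule on when the memo is signed and what its authors may have seen.

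Three stronger readings are tempting and should not be adopted.

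- **That sponsor unblinding is the route to a chosen threshold.** Appendix 7 Section 9.2 does say: "Selected members of the Sponsor study team may be unblinded to review the data from the Main Study Period". Those are data to Week 24, not off-treatment data. The durability proportion pools all entrants, so treatment codes are not needed to compare values of X. Main Section 9.2 also provides a separate blinded team for the Extension and excludes unblinded staff from later review of individual participants' data. That safeguard is partial, since it does not mention the memo, but it weakens this reading.
- **That the sponsor plans to fix the cut-off after seeing the data.** The text permits late finalisation; it does not plan it.
- **That every durability result hangs on one unset number.** Time to first use of a cough medication does not depend on X. The on-treatment example, that "a participant has a Week 52 measurement at least X-mm lower than the Week 0 measurement", belongs to a secondary exploration for which several response definitions are already foreseen.

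**Conclusion.** The point holds for the X% cut-off in the primary durability metric and for the definition of loss in the two time-to-loss endpoints. The documents allow these to be set when most off-treatment data may exist (60% to 77% complete three months before the end, under the two assumed entry patterns), and they do not bar the authors from those data. Across the assumed distributions (mean retained response 50% to 70%, SD 30% to 50%), moving X from 20% to 50% shifts the proportion by about 23 to 38 points. That is roughly three to five times the 8-point half-width at 150 participants. The shift shrinks if many participants fail by needing cough treatment.

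The consequence is limited to how far the durability estimate can be read as prespecified. The Week 24 analyses and their Type I error control are unaffected.

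**What to change.** Change the deadline in Appendix 7 Section 9.4. The memo should be finalised and dated before any off-treatment data are reviewed, ideally before the first participant enters, and should state that its authors have no access to those data. It should give, for each questionnaire, the numeric X% and the direction that counts as worsening (higher for VAS and CSD, lower for LCQ), and the definition of loss of response for the time-to-event endpoints.

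Tying the memo to Main-period unblinding would not be enough. Appendix 7 Section 9.2 expects the durability period to be under way when the Main period completes, so off-treatment data would already be accruing.

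If the earlier date is no longer achievable, report the proportion over a prespecified grid of X and label any later threshold post hoc.

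The cost is an earlier sign-off of a memo already planned. Sample size, visits and data collection do not change.

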## 9.5 Analysis Populations

Analyses will generally be based on All Subjects Enrolled.

### 9.6.1 Statistical Methods for Efficacy Analyses

For each ePRO separately, the proportion of participants who maintain treatment response during the 12-week off-treatment period will be estimated and the associated 95% CI will be calculated using the Clopper-Pearson method.

Time-to-event endpoints will be summarized using Kaplan-Meier estimates.

### 9.6.2 Statistical Methods for Safety Analyses

In the beginning of the Off-treatment Durability Study Period, up to 14 days after the last dose of study intervention, AE collection will follow the same process as in the Main and Extension Study Periods and will be analyzed with the AEs from the Main and Extension Study Periods in the CSR.

For the Off-treatment Durability Study Period, post 14 days after the last dose of study intervention, only drug-related SAEs, SAEs considered to be study participation related, drug-related NSAEs, and any pregnancy that is brought to the attention of the investigator will be collected. While such events will not be considered treatment emergent, they will be summarized in a separate report.

